9.7.10. Methods to control for confounding

Covariate-adjusted analysis. A multivariable model adjusted for baseline covariates will be the primary method to control for confounding. These include the demographic (age, sex, race, US region), vaccination or preventive care visit (calendar year/month, care setting), comorbidities and immunocompromising conditions. The list of covariates to be evaluated are detailed in Section 9.3.4. Variables between the RZV exposed and the RZV unvaccinated comparators that differ by a standardized mean difference greater than 0.10 will be adjusted for in the statistical models. The standardized mean difference is preferred over a p-value metric that can be influenced by large sample sizes when in fact there is little meaningful difference between groups.

Propensity score methods for the cohort design analysis. We may consider using propensity score methods to correct for imbalance in confounders between RZV exposed and RZV unvaccinated comparators. A logistic regression model will be used to estimate the conditional probability of receiving the RZV vaccine predicted by the baseline covariates observed in the 365 days preceding the start of follow-up (i.e., index date) and that were listed in Section 9.3.4. Variables are selected empirically based on a statistically significant association, as determined from bivariate analyses, between the confounder and the exposure and the confounder and the outcome of interest.

We will select the propensity score implementation method, such as inverse probability of treatment weighting, that yields the best covariate balance between the groups³⁵. To determine whether the propensity score method adequately addressed imbalances in covariates, we will evaluate the standardized mean differences between RZV vaccinated and RZV unvaccinated comparators less than 0.10, i.e., indicative of good confounder balance.

Bias analysis to test for unmeasured confounders for the cohort design analysis. One assumption underlying the cohort analyses is that there are no unobserved confounders related to RZV exposure and the study outcomes of interest, given the observed covariates. Unobservable factors, related to illness severity and health status, could influence RZV receipt and the outcomes of interest. The goal of the bias analysis is to estimate the magnitude of effect an unobserved confounder needed to change the statistical inference³⁶⁻³⁸.

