9.3. Variables

9.3.1. Exposure measure

RZV exposure will be defined as receipt of at least one dose of RZV for the primary analyses; per-dose analyses will be performed in secondary analyses. RZV vaccination will be identified by means of the national drug code (NDC) and by the Current Procedural Terminology (CPT) code. Part D generally pays for commercially available vaccines. The NDCs from the prescription drug events (PDE) file that will be used to identify RZV exposure as a prescription dispensing in an outpatient pharmacy setting are: 58 160-0828-01; 58 160-0829-01; 58 160 082 311; 58 160-0828-03; 58 160-0829-03; 58 160 082 311; and 58 160-0823-11. The CPT code 90750 for RZV will identify vaccine administration in a Part B (physician office setting) claim. It is anticipated that most will be identified from the PDE file and should only occur in one of the claims files since Medicare will not pay for the same vaccine administration twice, i.e., exposure will not be counted twice.

RZV vaccination records occurring within 27 days after a previous RZV vaccination record (i.e., on days 1-27, where the day of the previous RZV record is day 0) will be considered a duplicate record and will be deleted. The *participant* will be retained for the analytic cohort. For *participants* who receive more than two doses of RZV, even after removal of possible duplicates, we will exclude from analysis RZV doses beyond two per study *participant*.

Preventive care visits for comparison with RZV vaccinations will be identified by means of CPT, ICD-10, and Healthcare Common Procedure Coding System (HCPCS) codes, as shown in Table 2. The presence of any of the below codes qualifies as an eligible "preventive care visit."

Table 2Preventive care visit description for the comparators in the cohort analyses

ICD10	HCPS	CPT	Code Description
			Routine Adult Annual Exam
		99386	Initial comprehensive preventive medicine evaluation and management of an individual including an age and gender appropriate history, examination, counseling/anticipatory guidance/risk factor reduction interventions, and the ordering of laboratory/diagnostic procedures, new patient; 40-64 years
		99387	Initial comprehensive preventive medicine evaluation and management of an individual including an age and gender appropriate history, examination, counseling/anticipatory guidance/risk factor reduction interventions, and the ordering of laboratory/diagnostic procedures, new patient; 65 years and older

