9.3.4. Potential confounding variables and effect modifiers

A confounder is defined as any variable that is associated with both the exposure and the study HOI. Since a confounder cannot be on the causal pathway from exposure to the outcome, all confounders will be captured in the 365 days preceding the index date, i.e., RZV Dose 1 and Dose 2 vaccination date and the RZV unvaccinated comparator preventive care visit for the cohort design. All confounders identified using Medicare enrollment and medical or prescription claims data will be used for covariate adjustment in multivariable models. Propensity score methods will be considered for confounding adjustment, depending on identified imbalances in the observed covariates between the exposed and comparator groups. Confounding variables defined by health care services and comorbidities will be identified using a combination of ICD-10, CPT and HCPCS codes.

- **Demographic variables** will include age, sex, and race and ethnicity (i.e., white, black, Asian, Hispanic, North American Native, and other/unknown based on the US government categories)
- **Healthcare service variables** will include admissions to skilled nursing facilities (SNFs), number of hospitalizations, number of ED visits and Durable Medical Equipment (DME) use. These will be considered to control for potential imbalances between RZV vaccinees and RZV unvaccinated comparators in health impairment requiring more intensive services. The place of service and revenue code on the claim are used to designate the type of service setting.
- **Preventive care services** will include receipt of age-recommended vaccine (e.g., influenza, pneumococcal, and tetanus, diphtheria, pertussis). These will be

considered to control for potential healthy adherer bias that could result in imbalances in healthcare services and prior health seeking behavior patterns between RZV vaccinees and RZV unvaccinated comparators. Table 2 lists the preventive care services. Since mammography, bone mineral density, and colorectal screening are criteria for the unvaccinated comparator selection, these are not included as confounders in the analysis.

- **Medical comorbidities specific to PMR/GCA**. Potential risk factors specific to these conditions may include:
 - Age, which is found to be the strongest risk factor;¹⁹
 - Female sex is found to be a risk factor;¹⁹
 - Race/ethnicity as a significantly lower incidence is reported in African, Asian, Latinos;¹⁹

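### Adjusting the primary Cox model for index-event care setting leaves the RZV hazard ratio resting on non-pharmacy doses only, and the SMD rule leaves open whether age is always adjusted for

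*Combined protocol and SAP*

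**What the plan says.** For PMR and GCA (and ION as a secondary outcome), section 9.7.10 states: "A multivariable model adjusted for baseline covariates will be the primary method to control for confounding". The covariates it then names include those of the index event, "vaccination or preventive care visit (calendar year/month, care setting". It refers onward ("The list of covariates to be evaluated are detailed in Section 9.3.4") and adds that variables "that differ by a standardized mean difference greater than 0.10 will be adjusted for in the statistical models".

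On exposure, section 9.3.1 uses NDCs in the prescription drug event (PDE) file to "identify RZV exposure as a prescription dispensing in an outpatient pharmacy setting", and a CPT code for doses given in a physician office. Of the two sources it says: "It is anticipated that most will be identified from the PDE file". No percentage is given. Comparator index visits are identified only from CPT, ICD-10 and HCPCS codes (Table 2).

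On risk factors for PMR and GCA, section 9.3.4 lists first "Age, which is found to be the strongest risk factor". It also says that all confounders identifiable in the enrollment and claims data "will be used for covariate adjustment in multivariable models". Section 9.1 likewise names age, sex and calendar time as adjusted for in the Cox model. Section 9.3.3 says only that some of its listed covariates will be used to adjust or stratify.

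**The concern.** A comparator's index event is a medical visit or a screening procedure and never a pharmacy dispensing. A pharmacy level of care setting can therefore occur only in the vaccinated group. A model with exposure and setting as main effects cannot separate RZV from pharmacy in those people. It attributes their outcome experience to the pharmacy term and estimates the RZV hazard ratio from the remaining doses. The model still converges to an RZV estimate, so nothing in the output need show that most vaccinees no longer inform it. The programming review in section 9.8 checks output against the protocol and would not object either.

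The second issue is the selection rule. An SMD threshold looks only at the association with exposure. If the SMD sentence is a filter, a strong predictor of the outcome with a small imbalance is left out, and at this sample size a small bias matters for a test of a hazard ratio of 1.

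**Working it through.** **1. The plan's own figures.** Table 5 uses baseline responses of 0.000405 (PMR) and 0.000092 (GCA), a 1:4 ratio, 6 months, 80% power and two-sided 0.05. The Poisson-regression formula is

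N = [1.96·√(1/(p(1−p))) + 0.8416·√(1/(1−p) + 1/(p·RR))]² / [T·rate·(ln RR)²]

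With p = 0.2 and T = 0.5 it gives 438,239 for PMR at RR 2 and 723,361 for GCA at RR 3, against the stated 438,239 and 723,362. The baseline responses therefore act as annual rates over half a year, with no allowance for correlation between exposure and covariates.

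**2. Expected events at the planned size.** Section 9.2.2 projects about 2 million exposed and 8 million comparators. At no effect:
- PMR: 0.000405 × 0.5 × 2M = 405 exposed; × 8M = 1,620 comparator.
- GCA: 0.000092 × 0.5 × 2M = 92 exposed; × 8M = 368 comparator.

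**3. What the model estimates.** Take setting as pharmacy versus other. Only three cells contain people:
- comparators, other: log rate = a
- vaccinated, other: log rate = a + b
- vaccinated, pharmacy: log rate = a + b + g

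The term g fits the third cell exactly, so b (the log RZV hazard ratio) is the contrast of the first two cells only. Example, assuming a 90% pharmacy share and true relative risks of 2 for pharmacy and 1 for other doses: without setting, 0.9 × 2 + 0.1 × 1 = 1.90; with setting, 1.00.

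**4. Would the SMD rule exclude setting?** With pharmacy share q in the exposed and 0 in comparators, SMD = q / √(q(1−q)/2). This is 1.4 at q = 51% and 6.2 at q = 95%, so setting enters the model whether it is named or selected.

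**5. Precision.** With s the non-pharmacy share (assumed values, since the plan gives none), the informative exposed events are s × 405 or s × 92 under no effect and are multiplied by the true HR otherwise. The detectable HR is at 80% power by an exact conditional binomial test, two-sided 0.05, keeping all 8 million comparators.

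| Non-pharmacy share | PMR exposed events (null) | PMR detectable HR | GCA exposed events (null) | GCA detectable HR |
|---|---|---|---|---|
| 100% (setting not in model) | 405 | 1.16 | 92 | 1.36 |
| 49% | 198 | 1.22 | 45 | 1.50 |
| 10% | 40.5 | 1.50 | 9.2 | 2.18 |
| 5% | 20 | 1.74 | 4.6 | 2.79 |

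At 5%, power is 95% for PMR at RR 2 and 86% for GCA at RR 3. A normal approximation with null event counts, exp[2.8·√(1/(s·E₁) + 1/E₀)], gives 1.17 and 1.39 in the first row but 1.87 and 3.72 in the last. The last-row values are too pessimistic, because exposed events rise with the hazard ratio.

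**6. Age left out.** All inputs here are assumed: SMD 0.09, age SD 7 years, incidence +7% per year. Log bias = 0.09 × 7 × 0.07 = 0.044, so HR = 1.045. The standard errors from step 2 are √(1/405 + 1/1620) = 0.056 (PMR) and √(1/92 + 1/368) = 0.117 (GCA). The bias is about 0.8 and 0.4 standard errors, and the two-sided type I error becomes about 12% and 7%. At SMD 0.10 with a hazard ratio per SD of 1.5, 2.0 or 2.5, the spurious HR is 1.04, 1.07 or 1.10.

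**The case against.** **Care setting is never defined.** Neither 9.3.3 nor 9.3.4 lists the setting of the index event, and the only coding text, in 9.3.4, concerns baseline health-service use. A coding without a pharmacy level would avoid the problem. This stands as a caveat. But 9.7.10 names the variable and ties it to the vaccination itself, and the plan's main distinction between RZV claims is pharmacy versus physician office.

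**A reader might infer that the cohort analysis becomes underpowered.** The documents do not support that. The stated targets are still met at a 5% non-pharmacy share, and that share is itself an assumption. Setting the 100,000 informative vaccinees in that case (5% of 2 million) against Table 5's 144,673 is not valid either: Table 5 assumes 1:4, and the ratio would then be 1:80.

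**A reader might also infer a positivity failure in the propensity score.** The score is optional. Section 9.7.10 limits it to covariates from the 365 days before index that are listed in 9.3.4, and index care setting is not among them.

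**Age may never drop out.** Sections 9.1 and 9.3.4 and the opening of 9.7.10 read as unconditional adjustment, and the SMD sentence does not say that only imbalanced variables are used. This stands: omission is one reading, not a stated plan. What remains is a conflict with the SMD sentence and with 9.3.3, which the plan does not resolve.

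**Conclusion.** The care-setting point holds, provided that setting is coded with a pharmacy level. The primary PMR and GCA hazard ratios would then describe only non-pharmacy doses and be uninformative about most vaccinees. This needs no assumed share beyond the plan's own expectation that pharmacy claims are the majority. The size of the precision loss does depend on the share. For GCA the detectable HR goes from about 1.4 to 1.5, 2.2 or 2.8 at 49%, 10% or 5% non-pharmacy; for PMR it goes from about 1.17 to 1.2, 1.5 or 1.74. The targets of RR 3 and RR 2 survive, so the main harm is the changed estimand.

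The SMD point is a lesser one. It is an unresolved conflict between sections which, on its unfavourable reading and under assumed inputs, biases the hazard ratio by about 4-5%. That is small against the target effects but not negligible for testing a hazard ratio of 1 with this many events.

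**What to change.** In section 9.7.10:
- Remove the care setting of the index event from the covariates of the outcome model. If setting is of interest, report pharmacy and office doses separately, each against the comparators.
- State that age, sex, race/ethnicity, region, calendar month and the confounders in 9.3.4 are always in the model, whatever their SMD.
- Keep the SMD as a description of balance only, and align 9.1, 9.3.3 and 9.3.4 with this rule.

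The cost is a change of wording before the models are programmed, plus somewhat more model parameters. With about 2,000 PMR events (405 + 1,620) and 460 GCA events (92 + 368) expected, the loss of precision is negligible.

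### If propensity scores are used for the cohort outcomes, the significance screen in Section 9.7.10 makes confounder retention depend on event count, so weak or uncommon GCA confounders would often be dropped from that optional analysis

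*Combined protocol and SAP*

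**What the plan says.** Section 9.7.10 sets out two routes to confounding control for the cohort outcomes.

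- **Primary route.** "A multivariable model adjusted for baseline covariates will be the primary method to control for confounding". Covariates that "differ by a standardized mean difference greater than 0.10 will be adjusted for in the statistical models". The stated reason is that "The standardized mean difference is preferred over a p-value metric that can be influenced by large sample sizes".
- **Optional route.** "We may consider using propensity score methods to correct for imbalance in confounders". If it is taken, a logistic model for RZV receipt draws on the Section 9.3.4 covariates, and "Variables are selected empirically based on a statistically significant association, as determined from bivariate analyses, between the confounder and the exposure". The sentence goes on to the outcome: the association must hold "between the confounder and the exposure and the confounder and the outcome of interest". The natural reading is that both associations must be significant. Balance is then judged by standardized mean differences below 0.10, but the text does not say whether that check covers every Section 9.3.4 covariate or only the selected ones.

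Section 9.3.4 adds two statements. "All confounders identified using Medicare enrollment and medical or prescription claims data will be used for covariate adjustment in multivariable models", which does not match the 0.10 threshold in Section 9.7.10. And "Propensity score methods will be considered for confounding adjustment, depending on identified imbalances in the observed covariates", so the optional route is linked to observed imbalance.

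**The concern.** The selection sentence brings back a p-value criterion one paragraph after the plan sets p-values aside as dependent on sample size. The two tests fail in opposite directions. With millions of people the exposure test is significant for almost any difference, so it does not select. With a rare outcome the outcome test has little power, so it can discard real risk factors. Whether a confounder enters the score then depends on how many events that outcome, dose or subset happens to have, and the choice is made after looking at the outcome.

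At stake is any propensity-score HR for GCA, and possibly ION. Section 9.3.4 ties the method to observed imbalance, which is when adjustment matters most. If the balance check covers only the selected variables, it can look satisfactory while a dropped factor remains imbalanced.

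**Working it through.** **1. Reproduce the plan's sample size.** Inputs from Section 9.5.2 and Table 5: 1:4 allocation (p = 0.2), 183 days (T = 0.5 year), two-sided alpha 0.05, 80% power, baseline 0.000092 for GCA and 0.000405 for PMR. The Poisson-regression formula is

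N = [1.96·√V0 + 0.842·√V1]² / (T · rate · ln(RR)²), with V0 = 1/(p(1−p)) and V1 = 1/(1−p) + 1/(p·RR).

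For GCA at RR 3, V0 = 6.25 and V1 = 2.917. N = 40.16 / (0.5 × 0.000092 × 1.207) = 723,361, against 723,362 in the plan. PMR at RR 2 gives 438,239, as stated. All nine rows of Table 5 match within 1. With T = 1 the GCA figure is halved to 361,681, so the baseline values act as yearly rates.

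**2. Events.** Section 9.2.2 projects a little more than 2 million exposed and 8 million comparators.

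- GCA, projected cohort, RR 1: 10,000,000 × 0.5 × 0.000092 = 460.
- GCA, minimum N, RR 1: 723,362 × 0.5 × 0.000092 = 33.
- GCA, minimum N, RR 3: 0.5 × 0.000092 × (578,689 + 3 × 144,673) = 47.
- PMR, projected cohort, RR 1: 10,000,000 × 0.5 × 0.000405 = 2,025.

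**3. Exposure test.** The standardized difference detectable with 80% power is 2.80 × √(1/2,000,000 + 1/8,000,000) = 0.0022. At the minimum GCA sample it is 0.008. Both are far below the plan's 0.10, so the outcome test is the binding one.

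**4. Outcome test.** The probability that a true confounder fails p < 0.05 is 1 − [Φ(z − 1.96) + Φ(−z − 1.96)], with z = ln(HR)·√(D·p(1−p)). D is the number of events. The prevalence p is taken in the population or among cases, p·HR/(1 − p + p·HR), which gives a range. HRs and prevalences are assumptions.

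Example: HR 1.3, p = 5%, D = 460. In the population z = 0.262 × √(460 × 0.05 × 0.95) = 1.23, a 77% miss. Among cases p = 6.4% and z = 1.38, a 72% miss.

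| Assumed confounder | GCA, 47 events | GCA, 460 events | PMR, 2,025 events |
|---|---|---|---|
| HR 1.3, prevalence 5% | 93% | 72–77% | 18–27% |
| HR 1.5, prevalence 6% | 88–90% | 31–46% | under 1% |
| HR 1.5, prevalence 20% | 76–80% | 3–6% | under 1% |
| HR 2.0, prevalence 5% | 71–82% | 1–10% | under 1% |

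**5. Effect on a propensity-score HR.** Omitting one binary confounder multiplies the HR by (1 + p1(HR − 1)) / (1 + p0(HR − 1)), where p1 and p0 are its prevalences in vaccinees and comparators. For HR 1.2–1.5, standardized differences 0.1–0.2 and prevalence 5–20%, the shift is about 0.4% to 4%.

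For several factors, take eight, each with prevalence 10% against 5% (pooled 6% at 1:4), all acting in one direction, at 460 events:

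- HR 1.3: the factor is 1.030/1.015 = 1.0148. The miss rate is 68–73%, so 5.4–5.9 of eight are dropped. 1.0148^5.4 to 1.0148^5.9 gives a shift of about 8–9%.
- HR 1.5: the factor is 1.050/1.025 = 1.0244. The miss rate is 31–46%, so 2.5–3.7 of eight are dropped. 1.0244^2.5 to 1.0244^3.7 gives a shift of about 6–9%.

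A broader illustrative set shows the dependence on events. It has 16 confounders (HR 1.2, 1.3, 1.5 and 2.0 crossed with prevalence 5, 10, 20 and 30%), each with standardized difference 0.15 in one direction. The bias factor left is 1.33 at 47 events, 1.15 at 230, 1.08 at 460 and 1.01 at 2,025.

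**The case against.** The strongest defence is that this is not the planned primary adjustment. That stands in full. A reader might infer that the study's adjusted GCA HR stays confounded; the documents do not support this. The multivariable model is primary, propensity scores are only something the team may consider, and the primary covariates follow the 0.10 rule (or all identified confounders, under Section 9.3.4). A factor with prevalence 10% against 5% has a standardized difference of about 0.19, so the primary model would adjust for it.

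A reader might also infer that most true confounders are lost. That fits 33–47 events at the minimum N, but not the projected cohort, where losses fall on weak or uncommon factors. Section 9.3.4 names age as the strongest PMR/GCA risk factor and also lists sex and race; common factors with sizeable effects are the likeliest to be kept. Nor should six of eight dropped, a rate that fits HR 1.3, be paired with HR 1.5 to reach 1.0244^6 = 1.16: at HR 1.5 only 2.5–3.7 of eight are dropped.

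The post-score balance check would expose a dropped, imbalanced covariate if it covers all of Section 9.3.4. The plan leaves this open, so the defence is possible but not secured. Different covariates for different outcomes are partly intended, since Section 9.3.4 lists PMR/GCA and ION factors separately. A single-factor shift of a few percent is also small beside the GCA target of RR 3.

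What remains is that the rule is stated, would apply whenever the method is used, and conflicts with the plan's own reasoning about p-values.

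**Conclusion.** The point holds for any propensity-score HR, chiefly for GCA. At about 460 null events the screen would drop a confounder of HR 1.3 and 5% prevalence about 72–77% of the time, and one of HR 1.5 and about 6% prevalence about 31–46%. Common confounders with HR 1.5 or more would mostly survive, and PMR is little affected. The resulting shift is about 0.4–4% for one factor and roughly 6–9% for several acting together at 460 events. It would be larger with fewer events; analyses smaller than the full cohort, such as Dose 2, would fall between the minimum-N and projected figures, but the documents do not allow them to be placed exactly.

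The event counts rest on the plan's rates and projected cohort. The covariate HRs, prevalences, imbalances and common direction are assumptions. The plan gives no ION rate or power target, so the ION effect cannot be quantified.

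Severity is minor to moderate, because the method is optional and the primary HR does not pass through this screen.

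**What to change.** In Section 9.7.10, replace the selection sentence with: *The propensity score will include all prespecified Section 9.3.4 confounders relevant to the outcome, regardless of bivariate significance with exposure or outcome.* State that the post-score check against a standardized mean difference of 0.10 covers all of these covariates. Reconcile Section 9.3.4 (all identified confounders enter the multivariable models) with Section 9.7.10 (only those above 0.10).

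The cost is a few sentences. The score is a logistic model for vaccination, and with millions of records the full covariate list is feasible. The statistical price is a slightly larger variance from including weak confounders.
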